15.1 Power for analysis of secondary variables

A summary of the assumptions and power for the primary and secondary efficacy parameters using the same unpublished study is shown in [Table 15-1](#) for binary endpoints and [Table 15-2](#) for continuous endpoints.

Table 15-1 Summary of power for binary endpoints

Endpoint	Response Rate		Power
	Secukinumab 150 mg (N=300)	Placebo (N=150)	
ASAS20	61.1%	28.4%	99%
ASAS40	36.1%	10.8%	99%
ASAS5/6	43.1%	8.1%	99%
ASAS partial remission	13.9%	4.1%	92%

Table 15-2 Summary of power for continuous endpoints

Endpoint	Mean change from baseline		Common standard deviation	Power
	Secukinumab 150 mg (N=300)	Placebo (N=150)		
hsCRP	-0.60	0.12	0.84	99%
Total BASDAI	-2.19	-0.85	2.10	99%

Endpoint	Mean change from baseline		Common standard deviation	Power
	Secukinumab 150 mg (N=300)	Placebo (N=150)		
SF-36 PCS	6.06	1.92	6.65	99%
ASQoL	-4.00	-1.37	4.45	99%

16 Appendix

16.1 Visit Windows

When visit windows are used, all visits will be re-aligned, i.e., they will be mapped into one of the visit windows. E.g., if the *Week 4* visit of a subject is delayed and occurs on Day 46 instead of on Day 29, it will be re-aligned to visit window *Week 8*. In the case of major deviations from the visit schedule, or due to unscheduled visits, several assessments of a subject may fall in a particular visit window (either scheduled or unscheduled). Statistical approaches to handle multiple assessments in a given visit window are specified below.

For lab/ECG/vital signs, follow-up (F/U) visit is excluded from analysis visit mapping window. Only assessments that come as F/U nominal visit will be directly assigned as analysis F/U visit. Other assessments that are beyond the last on-treatment visit window (W60) or after nominal F/U visit date won't be mapped to any analysis visit. F/U visit will not be included in the summary tables by visit.

Of note, subjects are allowed to have gaps in visits. All data collected will be displayed in listings.

Table 16-1 Analysis visit windows

Analysis Visit	Target Day	Analysis Visit Window	Group 1	Group 2	Group 3	Group 4	Group 5	Group 6
Baseline	1	≤ 1	≤ 1	≤ 1	≤ 1	≤ 1	≤ 1	≤ 1
Week 1	8	2-11	2-11					
Week 2	15	12-18	12-18	2-22				
Week 3	22	19-25	19-25					
Week 4	29	26-43	26-43	23-43	2-71			2-57
Week 8	57	44-71	44-71	44-71				
Week 12	85	72-99	72-99	72-99				58-99
Week 16	113	100-127	100-127	100-127	72-141	2-141	2-239	100-141
Week 20	141	128-155	128-155	128-155				
Week 24	169	156-183	156-197	156-197	142-267	142-267		142-197
Week 28	197	184-211						
Week 32	225	212-239	198-253	198-253				198-253
Week 36	253	240-267						
Week 40	281	268-295	254-323	254-323				254-323
Week 44	309	296-323						
Week 48	337	324-351						
Week 52	365	352-379	324-379	324-379	268-379	268-379	240-379	352-379
Week 56	393	380-407						
Week 60	421	408-435	380-435	380-435	380-435	380-435	380-435	380-435

Group1: Patient's global assessment of disease activity (VAS), Patient's assessment of back pain intensity (VAS), BASFI, BASDAI, Vital signs, hematology, blood chemistry, urinalysis

Group2: [REDACTED] hsCRP

Group3: SF-36, [REDACTED] [REDACTED], [REDACTED], ASQoL, [REDACTED] Lipids

The following rules are used to determine the window for an applicable visit post baseline: “Lower limit” = “upper limit of prior applicable visit” + 1. “Upper limit” = “target day of current visit” + integer part of (“target day of next applicable visit” – “target day of current visit”)/2. Lower limit of the first applicable visit is always Day 2.

The mapping described above applies to all visits (not just scheduled visits). Repeat and/or unscheduled visits (which will be numbered in the database according to new NCDS standards) will be mapped for analysis purposes in the same way as scheduled visits. This leaves the possibility, then, for multiple measurements within an analysis window. The following conventions will be used to determine the appropriate measurement to be summarized in the event of multiple measurements within a visit window.

Table 16-2 Rules for flagging variables

Timing of measurement	Type of data	Rule
Baseline	All data	
The last measurement made prior to administration of the first dose of study treatment – note this may include measurements taken on the day of randomization (e.g. lab). Baseline assessments scheduled for and captured on Day 1 will be considered baseline measurements regardless of the time of assessment. If a patient did not receive any dose of study treatment then the randomization date will be used.
 
Only the date part will be considered if there is only one assessment on Day 1 but if there are multiple assessments on Day 1, then the following rules will apply:
 
1. If time of assessment exist,
• select the last available measurement prior to the reference start date/time considering time• if no measurement prior to the reference start date/time then considering time select the earliest measurement post reference start date/time2. If time of assessment does not exist the measurement from the lowest CRF visit number will be used.
Post-baseline efficacy	All data	
The measurement closest to the target day will be used. In the event two measurements are taken equally apart (e.g. 1 day before target date and 1 day after) the first one will be used. If the patient switches from placebo to AIN within the window the following rules apply:
 
1. If the analysis visit window is \leq week 16, then
• If available, the closest measurement to the target date which is on or before the switch date will be used• If there are no data on or before the switch then the closest measurement after the switch to target will be used2. If the analysis visit window is $>$ week 16, then
• If available, the closest measurement to the target date which is after the switch date will be used• If there are no data after the switch then the closest to target before or on the switch date will be used 
Cases where the same parameter is recorded more than once on the same date will be handled as follows:
 
• If time of completion exists the earliest measurement will be used• If time does not exist the measurement from the lowest CRF visit number will be used
Post-baseline safety	Summary visit information (e.g. lab, ECG, etc.)	
The measurement closest to the target day will be used. In the event two measurements are taken equally apart (e.g. 1 day before target date and 1 day after) the first one will be used. If the patient switches from placebo to AIN within the window the following rules apply:
 
1. If the analysis visit window is \leq week 16, then

Timing of measurement	Type of data	Rule
		
• If available, the closest measurement to the target date which is on or before the switch date will be used• If there are no data on or before the switch then the closest measurement after the switch to target will be used 
2. If the analysis visit window is > week 16, then
 
• If available, the closest measurement to the target date which is after the switch date will be used• If there are no data after the switch then the closest to target before or on the switch date will be used 
Cases where the same parameter is recorded more than once on the same date will be handled as follows:
 
• If time of completion exists the earliest measurement will be used• If time does not exist the measurement from the lowest CRF visit number will be used• If CRF visit number is the same the average value will be used
Post-baseline safety	Notable abnormalities (e.g. lab)	The most extreme measurement in the window will be used. Note this means a patient can have a notably high and notably low measurement within a window

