5.5.4 Instructions for prescribing and taking study treatment

All study treatment (150 mg secukinumab/placebo) will be self-administered by the subject subcutaneously throughout the study, at the study site, after the study assessments for the visit have been completed. Site staff will administer the injection only to those subjects who feel insecure to self-administer the PFS injection.

Detailed instructions for self-administration of the study treatment will be given in the instructions for use (IFU) provided to each subject. Self-injection will take place under the supervision of a site staff member. At the randomization visit, the subject will be instructed by the site staff, utilizing the IFU on how to self-inject via prefilled syringes. Subjects will be asked to raise questions, if they have any, and then to proceed with self-injection of the study drug.

The first study treatment administration will occur at the randomization visit after the inclusion/exclusion criteria have been confirmed, all study scheduled assessments have been performed and the scheduled blood samples have been drawn.

At study visits when pre-dose blood has to be drawn ([Table 6-1](#)), the subject will self-inject the study treatment only after blood samples have been taken. All dates and times of injections self-administered by the subject during the study must be recorded in the Dosage Administration Record eCRF. Immediately before dispensing the package to the subject, investigator staff will detach the outer part of the label from the packaging and affix it to that subject's source document (Drug Label Form).

Once the s.c. injection has been completed and the condition of the subject is deemed stable by the investigator or designated healthcare professional, the subject can be discharged

The investigator should promote compliance by instructing the patient to attend the study visits as scheduled and by stating that compliance is necessary for the patient's safety and the validity of the study. The patient should be instructed to contact the investigator if he/she is unable for

any reason to attend a study visit as scheduled or if he/she is unable for any reason to take the study treatment as prescribed.

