5.5.14 Early study termination

The study can be terminated at any time for any reason by Novartis. Should this be necessary, the patient should be seen as soon as possible and treated as for a prematurely withdrawn patient. The investigator may be informed of additional procedures to be followed in order to ensure that adequate consideration is given to the protection of the patient's interests. The investigator will be responsible for informing the Institutional Review Board/Independent Ethics Committee (IRBs/IECs) of the early termination of the trial.

6 Visit schedule and assessments

[Table 6-1](#) list all of the assessments and indicate with an "X" when the visits are performed.

Subjects should be seen for all visits on the designated day, or as closely as possible to the originally planned visit schedule.

For visits scheduled through Week 4, the study treatment should not be administered within less than 7 days after the previous administration.

For visits scheduled after Week 4, the study treatment should not be administered within less than 14 days after the previous administration.

Subjects who prematurely discontinue study treatment should return for the end of treatment visit (4 weeks after the last study treatment administration), as well as return for the follow-up visit (F60), 12 weeks after last study treatment administration.

If they refuse to return for these assessments or are unable to do so, every effort should be made to contact them or a knowledgeable informant by telephone to determine the reason.

Screening will be flexible in duration based on the time required to wash out prior anti-rheumatic medications and will have a duration of up to 10 weeks, during which time the subject will sign the ICF, be evaluated for eligibility and allowed sufficient time for potential medication washout, in addition to all other assessments indicated in [Table 6-1](#).

Screening will consist of two consecutive visits. During Screening visit 1, initial assessments will be performed as outlined in [Table 6-1](#). At that visit, the duration of the washout period will be determined and Screening Visit 2 will be performed as follows:

- If the washout period is \leq 4 weeks, the investigator should proceed directly to Screening visit 2 on the same day and complete all assessments prior to randomization in the next 4 weeks.

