11.3 Handling of missing data

Missing data for ASAS20/40 response and other binary efficacy variables (e.g., ASAS5/6, etc.) for data up to Week 16 will be handled as follows:

1. Patients who drop out of the trial for any reason will be considered as non-responders from the time they drop out through Week 16.
2. Patients who do not have the required data to compute responses (e.g., ASAS components) at baseline and at the specific timepoint will be classified as non-responders at the specific timepoint.

Patients who are unblinded prior to the scheduled timepoint will be considered non-responders from the time of unblinding up to Week 16. The primary analysis will use non-responder imputation.

Continuous variables (e.g., ASAS components) will be analyzed using a mixed-effects model repeated measures (MMRM) which is valid under the missing at random (MAR) assumption. As such, single-point imputation of missing data will not be performed (e.g., LOCF). For analyses of these parameters, if all post-baseline values are missing then these missing values will not be imputed and this patient will be removed from the analysis of the corresponding variable, i.e., it might be that the number of patients providing data to an analysis is smaller than the number of patients in the FAS. Model will be based on randomized treatment (Week 1 to Week 16).

Data collected after Week 16 will generally be presented as ‘observed case’; i.e. all available data for each time point will be included in the analyses.

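### Visits are labelled by study day, so a late pre-dose Week 16 assessment becomes Week 20: an on-placebo value can be reported as a post-switch result, and some assessed patients count as Week 16 non-responders

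*SAP*

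**What the plan says.** - **Labelling.** SAP 16.1 states that "When visit windows are used, all visits will be re-aligned, i.e., they will be mapped into one of the visit windows". The rule covers repeat and unscheduled visits too. The SAP's own illustration moves a delayed Week 4 visit on Day 46 to Week 8.
- **Windows.** The Table 16-1 row reads "Week 16 113 100-127 100-127 100-127" for the general window, Group 1 (patient global, back pain, BASFI, BASDAI) and Group 2 (including hsCRP). Week 20 is Days 128-155 in both groups. Group 3 (including SF-36 and ASQoL) has a Week 16 window of Days 72-141.
- **Switch within a window.** Table 16-2 chooses among values inside one window. For windows after Week 16 it prefers post-switch values, but adds: "If there are no data after the switch then the closest to target before or on the switch date will be used".
- **Missing responses.** SAP 11.3 says that patients without the data needed for a response at baseline and "at the specific timepoint will be classified as non-responders at the specific timepoint". The MMRM uses Weeks 1 to 16. Later data are generally shown as observed cases.
- **Timing of visits.** Protocol Section 6: "Subjects should be seen for all visits on the designated day, or as closely as possible to the originally planned visit schedule". The text gives no limit in days on lateness.
- **Order within a visit.** Protocol 5.5.4 has the injection given "after the study assessments for the visit have been completed". Protocol 3.1 starts secukinumab in the placebo arm at Week 16.

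**The concern.** Labelling by day does little harm between two visits on the same treatment. Here the boundary between Week 16 and Week 20 lies next to the treatment switch, and the switch follows the visit, not the calendar. A patient whose Week 16 visit is 15 or more days late is assessed first and receives the first open-label dose afterwards. The assessment is pre-switch, but its label says Week 20.

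The Table 16-2 switch rules do not repair this, because they act only inside a window and cannot return a Day 128 value to Week 16. For a placebo patient the fallback then places an on-placebo value in the open-label course. In both arms the patient can lack Week 16 ASAS data even though the Week 16 visit took place, and the plan scores that as failure. From a visit on Days 128-141, SF-36 and ASQoL still count as Week 16, so one visit is present for two endpoints of the test sequence and absent for the other six.

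At stake are the accuracy of the Week 20 summary in the switch sequence and, to a small degree, the Week 16 response rates.

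**Working it through.** **1. Reproduce the windows.** SAP 16.1 sets the upper limit at target + int((next target - target)/2), and the lower limit at the prior upper limit + 1.

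- Groups 1 and 2, Week 12 upper: 85 + int((113 - 85)/2) = 99, so Week 16 starts on Day 100.
- Week 16 upper: 113 + int((141 - 113)/2) = 127.
- Week 20: Day 128 to 141 + int((169 - 141)/2) = 155.
- Week 24 therefore starts on Day 156.
- Group 3 has no Week 20 assessment, so its Week 16 upper limit is 113 + int((169 - 113)/2) = 141.

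All agree with Table 16-1. Day 128 is 128 - 113 = 15 days after target.

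**2. Follow a late Week 16 visit in the placebo arm.**

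| Week 16 visit (assess, then switch) | Label, Groups 1 and 2 | Next visit | Its label | Value reported as Week 20 |
|---|---|---|---|---|
| Day 127 | Week 16 | Day 155 (+28) | Week 20 | post-switch |
| Day 128 | Week 20 | Day 156 (+28) | Week 24 | on-placebo |
| Day 130 | Week 20 | Day 158 (+28) | Week 24 | on-placebo |
| Day 141 | Week 20 | Day 169 (+28) | Week 24 | on-placebo |
| Day 130 | Week 20 | Day 144 (+14) | Week 20 | post-switch |
| Day 156 | Week 24 | Day 184 (+28) | Week 24 | none in window |

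With four-week spacing after the late visit, the on-placebo value is the only one in the Week 20 window and the fallback selects it. If the next visit comes sooner (14 days is the minimum dosing gap in Protocol Section 6), the post-switch value is used and the late Week 16 value enters no by-visit analysis.

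**3. Consequence at Week 16.** If nothing else falls on Days 100-127, the four main ASAS domains have no Week 16 value. SAP 11.3 then gives non-response for ASAS20, ASAS40, ASAS 5/6 and partial remission. BASDAI and hsCRP are missing at Week 16 in the MMRM, not failures.

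**4. Size.** Inputs from SAP 15 and 15.1: 300 v 150 patients; ASAS20 61.1% v 28.4%; partial remission 13.9% v 4.1%. Let f be the share of patients in each arm who are scored as failures for this reason. The documents do not give f, so it is an assumption. If these patients would otherwise respond at the planned rates, each rate is multiplied by (1 - f).

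| f | Secukinumab | Placebo | Difference (points) | Odds ratio |
|---|---|---|---|---|
| 0 | 61.1% | 28.4% | 32.7 | 3.96 |
| 1% | 60.5% | 28.1% | 32.4 | 3.91 |
| 2% | 59.9% | 27.8% | 32.0 | 3.87 |
| 5% | 58.0% | 27.0% | 31.1 | 3.74 |

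**5. Power.** Exact two-sided Fisher power at f = 0 is above 99.9% for ASAS20 (stated: 99%) and 93.1% for partial remission (stated: 92%). ASAS20 power stays above 99.9% at f = 5%. Partial remission falls to 92.5% at f = 2% and 91.6% at f = 5%. If the two-sided p is taken as twice the one-sided p, the corresponding figures are 91.9%, 91.3% and 90.2%.

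**The case against.** The case for leaving the plan alone is substantial.

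- **Day-based windows are a disclosed convention.** The SAP explains the rule and illustrates it with a delayed visit. The longer window for SF-36 and ASQoL follows from the same formula, because neither is scheduled at Week 20. This stands. A reader might infer that the SAP accepts Day 141 as a tolerance for Week 16. It does not: that limit only reflects sparse scheduling.
- **Not every late patient becomes a non-responder.** If the whole schedule slips (Week 12 on Day 102, Week 16 on Day 130), the Week 12 assessment is labelled Week 16 and the patient is scored on real data. This stands, and f counts only patients with nothing on Days 100-127.
- **A late value is not a clean 16-week value.** After an on-time Week 12 dose on Day 85, a visit on Days 128-141 comes 128 - 85 = 43 to 141 - 85 = 56 days after the last injection, against a four-week interval. Scoring a large schedule deviation as failure can be a deliberate, conservative choice. This is a good reason not to change the primary derivation.
- **Sensitivity analyses for missing ASAS20 data are already named.** SAP 11.4 lists multiple imputation and observed-data analysis. This helps in part: they are optional, cover ASAS20 only, and neither is specified to use the late assessment itself.
- **The Week 20 error enters no hypothesis test.** This is correct, because inferential comparison stops at Week 16. The reported summary is still wrong where the fallback applies.

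**Conclusion.** The fallback in Table 16-2 gives a wrong result as written: it can present a value obtained on placebo as a result after the switch to secukinumab. The error is confined to descriptive data and to placebo patients who switch on Days 128-155 with no post-switch value in that window.

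The Week 16 effect is real but small. Under an assumed f of 1% to 5%, equal in both arms, the ASAS20 difference falls by 0.3 to 1.6 points, in the conservative direction. This rests on late patients responding at the planned rates, which the overdue dose makes uncertain.

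Two stronger readings are not supported. One is that the primary conclusion is in danger; ASAS20 power stays above 99.9%. The other is that type I error is inflated. That needs lateness to differ between arms. In an extreme case with no true effect, a common response rate of 61.1% and 5% late in the placebo arm only, Fisher rejection would rise from 4.3% to 8.1%. Nothing in the documents suggests such a pattern under blinding.

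**What to change.** 1. In Table 16-2, for windows after Week 16, delete "If there are no data after the switch then the closest to target before or on the switch date will be used". A value on or before the switch date is then never shown as post-switch, and the visit stays missing under the observed-case rule of SAP 11.3. The efficacy and by-visit safety rows both carry the sentence and should agree.
2. Pre-specify, before the Week 16 unblinding, a sensitivity analysis of ASAS20 and the other Week 16 endpoints in the test sequence, with the same rule in both arms. When Days 100-127 hold no assessment made on or before the first open-label dose, use the pre-dose assessment of the nominal Week 16 visit. Apply non-responder imputation to the ASAS endpoints only if that is absent too.
3. Report by arm how many patients this affects, which replaces the assumed f with a count.

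The primary derivation stays as it is. The cost is SAP wording, one extra analysis, and a few Week 20 values left missing.

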16.2 Statistical methodology and assumptions

16.2.1 Analysis of continuous data

16.2.1.1 Summary statistics for continuous data

Summary statistics (including N, mean, standard deviation, minimum, lower quartile, median, upper quartile, maximum) will be provided for continuous data by visit and treatment group.

16.2.1.2 Analysis of covariance

Univariate model

An analysis of covariance (ANCOVA) model will be used to analyze some endpoints. The model will include factors and covariates as specified for respective analysis. The SAS code below outlines a template for the analysis where covariates can be added or removed as required:

```
ods output diff=lsmeans=lsmeans;
proc mixed data=;
by visit;
class treatment strata;
model outcome = treatment strata baseline weight;
lsmeans treatment / diff cl;
run;
```

Least-square-mean (LSM) estimates for each treatment group and LSM difference, confidence intervals and p-value for the difference between secukinumab and placebo can be obtained.

Repeated measures analysis

Some endpoints will be analyzed using a longitudinal model that comprises several visits. The model used will be mixed model repeated measures (MMRM) with factors, covariates, interactions and covariance structure as specified for respective analysis. The SAS code below outlines a template for the analysis where covariates and interaction terms can be added or removed as required:

```
ods output diff=lsmeans=lsmeans;
proc mixed data=;
class treatment strata visit;
model outcome = treatment strata visit baseline weight treatment*visit baseline*visit / ddfm=kr;
repeated visit / type=un subject=;
lsmeans treatment*visit / diff cl;
run;
```

Least-square-mean (LSM) estimates for each treatment group and LSM difference, confidence intervals and p-value for the difference between secukinumab and placebo will be calculated at appropriate analysis visits.

In case the MMRM model does not converge the following sequential steps will be used:

1. change to type=cs. If still no convergence, perform step 2.
2. remove covariates in the following order until convergence: *weight, baseline*visit, strata*.

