Between-treatment differences in the change from baseline in BASDAI will be evaluated using a mixed-effect model repeated measures (MMRM) with treatment group, analysis visit, and randomization stratum (region) as factors, baseline BASDAI score and baseline weight as continuous covariates. Treatment by analysis visit and baseline BASDAI score by analysis visit will be included as interaction terms in the model. An unstructured covariance structure will be assumed for the model. The significance of the secukinumab treatment effect at Week 16 will be determined from comparison performed between secukinumab regimen and placebo at Week 16.

SF-36 PCS and ASQoL at Week 16

[figure not shown]
See [Section 11.7](#).

[figure not shown]
ASAS partial remission at Week 16

Response at Week 16 to ASAS partial remission criteria will be evaluated using a logistic regression model with treatment, randomization stratum (region) as factors and baseline weight as a covariate. Odds ratios and 95% CI will be presented for comparison performed between secukinumab regimen and placebo at Week 16.

Sensitivity analysis for hierarchy variables using patient's global assessment of disease activity (VAS)

During the data cleaning review process prior to database lock, a patient was found to have had a baseline value for “patient’s global assessment of disease activity (VAS)” completed out of sequence during a post-baseline visit, as documented in the vendor’s audit trail. Since this variable is a component of ASAS20, ASAS40 and ASAS 5/6 that require the calculation of change from baseline, a sensitivity analysis using the same logistic regression analysis for these hierarchy variables excluding this baseline value will be done.

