13.6 Compound specific safety evaluation

Safety topics of interest, such as risks defined in the Safety Profiling Plan (SPP), Risk Management Plan or topics of interest regarding signal detection or routine analysis are defined in the Program Case Retrieval Sheet that is stored in CREDI at the path Cabinets/CREDI Projects/A/AIN457A/Integrated Medical Safety.

The crude incidence and exposure-adjusted incidence rates for SPP risks will be summarized. In addition, listings will be provided presenting which subjects experienced which risk.

Important note: For the evaluation of SPP risks primary and secondary system organ classes of the MedDRA dictionary will be considered.

14 Interim analyses

The primary analysis will be performed after all subjects have completed the Week 16 visit in order to support regulatory filing. As the primary analysis is scheduled at Week 16, no adjustments will be made to the testing strategy to control the family-wise type I error. The investigators, site personnel and monitors will continue to remain blinded to the treatment each subject received at randomization all patients have completed the study (Week 60 Follow up) and the final database lock has occurred. Additional analyses may be performed to support interactions with health authorities, as necessary.

15 Determination of sample size

The sample size calculation is driven by the patient exposure requirements in the study population. An overall type I error (2-sided) 5% will be used to control type I error. Secukinumab 150 mg regimen will be tested versus placebo with respect to the primary endpoint (ASAS20 response at Week 16). A sample size of 300 patients in secukinumab 150 mg group and 150 patients in placebo group (randomization ratio = 2:1) is chosen in order to expose 300 patients to secukinumab for safety evaluation and also to achieve adequate power for the primary and secondary endpoints for this study.

Analysis of an unpublished phase III study showed a placebo response rate of about 28.4% and active drug response rate of 61.1% after 16 weeks for ASAS20. Using these assumptions, overall, the power for the ASAS20 endpoint should be about 99% with 300 patients in secukinumab 150 mg group and 150 patients in placebo group based on Fisher's exact test (nQuery Advisor 7.0).

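### If the unstructured MMRM does not converge, the SAP goes straight to compound symmetry with model-based errors, so the Week 16 standard error is wrong whenever residual variance differs by visit

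*SAP*

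**What the plan says.** SAP 11.5 and 11.7 analyse hsCRP, BASDAI, SF-36 PCS and ASQoL with an MMRM. For each the text is explicit: "An unstructured covariance structure will be assumed for the model". SAP 11.3 limits the model to Weeks 1 to 16 on randomized treatment.

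SAP 16.2.1.2 gives the PROC MIXED template, with an unstructured covariance and Kenward-Roger degrees of freedom. It has no option for empirical standard errors. The contingency follows: "In case the MMRM model does not converge the following sequential steps will be used". Step 1 is "change to type=cs. If still no convergence, perform step 2". Step 2 drops weight, then baseline-by-visit, then the stratum. No structure with visit-specific variances stands between unstructured and compound symmetry.

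SAP section 5 asks for the primary and secondary endpoints by region, and for analyses by prior TNF inhibitor use in the total and the Chinese population.

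**The concern.** Homogeneous compound symmetry has two parameters: one variance for all visits and one correlation for all pairs of visits. An unstructured matrix for seven visits has 7 × 8 / 2 = 28. The two-parameter model will rarely fail, so step 1 would in practice be the final model.

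The treatment contrast of interest is at one visit, Week 16. Under compound symmetry its standard error is built from the pooled variance over visits. If Week 16 is more variable than the earlier visits, the standard error is too small and the interval too narrow. If it is less variable, the reverse holds. Kenward-Roger adjusts for estimating the covariance parameters within the chosen structure; it does not repair a wrong structure.

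The four MMRM endpoints are H3, H5, H6 and H7 in a fixed sequence that is said to hold family-wise error at 5%. A contingency that can miss its nominal level is a weak point in that claim, even if it is seldom used.

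**Working it through.** **Inputs from the documents**
- Two-sided 5% level (SAP section 15): "An overall type I error (2-sided) 5% will be used to control type I error".
- Group sizes (SAP section 15): "A sample size of 300 patients in secukinumab 150 mg group and 150 patients in placebo group (randomization ratio = 2:1) is chosen".
- SAP Table 15-2 (mean change on secukinumab, on placebo, common SD, power): "Total BASDAI -2.19 -0.85 2.10 99" and "hsCRP -0.60 0.12 0.84 99". SF-36 PCS: difference 6.06 − 1.92 = 4.14, SD 6.65. ASQoL: difference 4.00 − 1.37 = 2.63, SD 4.45.
- Visits up to Week 16: BASDAI at Weeks 1, 2, 3, 4, 8, 12 and 16 (Protocol Table 6-1; SAP Table 16-1, Group 1). hsCRP has five analysis windows, Weeks 2, 4, 8, 12 and 16 (Group 2). SF-36 and ASQoL have Weeks 4 and 16 only (Group 3).
- Dropout of 10% by the primary endpoint (Protocol section 4).

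**Assumed, because the documents give no SDs by visit:** the SD changes linearly by visit from r × SD16 at the first visit to SD16 at Week 16.

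**The plan's own figures.** SE = SD × √(1/300 + 1/150) = SD × 0.10. The expected z is the difference divided by the SE:
- hsCRP 0.72 / 0.084 = 8.6
- BASDAI 1.34 / 0.210 = 6.4
- SF-36 PCS 4.14 / 0.665 = 6.2
- ASQoL 2.63 / 0.445 = 5.9

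Power, Φ(z − 1.96), exceeds 99.99% for all four, consistent with the stated 99%. At 270 versus 135 (10% dropout) it stays above 99.9%.

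**The fallback.** With complete data:
- reported SE / correct SE = √(mean of the visit variances / Week 16 variance)
- for K visits with a linear SD path, mean variance / SD16² = ((1 + r)/2)² + (1 − r)² (K + 1) / (12(K − 1))
- actual alpha = 2 × (1 − Φ(1.96 × ratio))

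For BASDAI, K = 7 and the second term is (1 − r)²/9. At r = 0.5: 0.5625 + 0.0278 = 0.5903; ratio √0.5903 = 0.768; alpha = 2 × (1 − Φ(1.506)) = 13.2%.

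| First-visit SD as share of Week 16 | SE ratio | BASDAI SE reported (correct 0.210) | Actual alpha |
|---|---|---|---|
| 0.5 | 0.768 | 0.161 | 13.2% |
| 0.6 | 0.811 | 0.170 | 11.2% |
| 0.7 | 0.856 | 0.180 | 9.4% |
| 0.8 | 0.903 | 0.190 | 7.7% |
| 0.9 | 0.951 | 0.200 | 6.2% |
| 1.0 | 1.000 | 0.210 | 5.0% |
| 1.25 | 1.128 | 0.237 | 2.7% |

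The path matters. If the SD grows linearly in weeks instead of by visit, alpha is 8.6% at r = 0.8 and 16.6% at r = 0.5. For hsCRP (K = 5, second term (1 − r)²/8) the by-visit path gives 7.7% and 13.1% at the same two values. For two visits (K = 2) it gives 7.6% and 12.1%.

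**Simulation.** The SAP model was fitted under compound symmetry by REML, with 300 versus 150 patients, seven visits, 10% monotone dropout, Week 16 SD 2.10 and 4,000 runs per growing-SD scenario. A normal reference replaced Kenward-Roger, which is immaterial at this size. Each range covers two true correlation patterns.

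| r | Type I error, model-based SE | Type I error, sandwich SE |
|---|---|---|
| 0.8 | 8.1%–8.6% | 5.1%–5.2% |
| 0.6 | 11.0%–12.0% | 5.1% |
| 0.5 | 13.5%–14.3% | 5.2%–5.6% |

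The Monte Carlo error is about 0.35 points at a true 5%. The equal-SD control with model-based errors gave 5.8%–6.2% in its first 4,000 runs and 5.0%–5.1% in a repeat of 5,000, pooled 5.4%–5.5%. Heterogeneous structures were not simulated.

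**The case against.** A reader might infer that the fallback inflates type I error in the confirmatory hierarchy as a matter of course. The documents do not support that, for four reasons.

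- **Direction.** Only one SD per endpoint is given, and it is the SD of the raw change. The model's residual SD, after baseline, baseline-by-visit, weight and region, may follow another pattern. Growth over visits is plausible but assumed; constant SDs give no error and falling SDs make the test conservative.
- **Trigger.** The hierarchy is tested in the full analysis set of about 450 patients, where failure of the unstructured model is unlikely. For SF-36 PCS and ASQoL, three covariance parameters over two visits make it barely credible. ASAS20 and the other responder endpoints use logistic regression and are untouched.
- **Consequence.** With expected z values of about 6 to 9, even a standard error 23% too small would rarely change a decision.
- **Subgroups.** Failure is more plausible in the region and prior-TNF analyses (about 450 − 360 = 90 patients outside China; TNF incomplete responders capped at 30%). These lie outside H1–H8, so the family-wise argument does not reach them.

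The SAP also fixes the order of its steps in advance, which limits discretion. And an uncorrected sandwich is no cure-all: in a simple complete-data approximation its type I error was about 5.9% at 60:30 and about 8% at an illustrative 18:9.

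All of this stands, and it limits the point to a minor one. It does not remove the defect: when the rule is used, it gives the wrong Week 16 standard error unless the pooled variance happens to equal the Week 16 variance.

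**Conclusion.** The point holds as a conditional, minor one. Two things must both occur: the unstructured model fails to converge, and residual variance differs by visit. For BASDAI, on a linear-by-visit SD path, a first-visit SD of 50%, 60%, 70% or 80% of Week 16 gives a standard error of 77%, 81%, 86% or 90% of the correct one and a two-sided alpha of about 13%, 11%, 9% or 8%. The SD path is an assumption, and the sign reverses if variability falls.

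It matters mainly for BASDAI and hsCRP, and for the subgroup analyses. What is at stake is chiefly the width of the reported intervals. The calculation does not show that family-wise error control fails in the planned full-set analysis.

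**What to change.** In SAP 16.2.1.2, replace step 1 with an ordered list that keeps visit-specific variances: heterogeneous Toeplitz, then heterogeneous AR(1), then heterogeneous compound symmetry, with Kenward-Roger retained for each. Place homogeneous compound symmetry last, just before covariates are removed. If it is reached, require an empirical (sandwich) standard error, with a small-sample correction in the subgroups, and degrees of freedom compatible with it. No sandwich is needed once a heterogeneous structure converges.

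Trying heterogeneous structures first is better than only adding a sandwich to the present step 1. SAP 11.3 relies on missing at random, and with dropout a badly wrong covariance can affect the estimate as well as its standard error; that effect was not quantified here.

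The cost is SAP wording, fixed before unblinding. The drawbacks are a slightly longer fallback list, and loss of Kenward-Roger only if homogeneous compound symmetry is reached.
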